10.4.8 Handling of Withdrawals or Missing Data

Patients withdrawn after only one treatment period will not be included in the pharmacodynamic analyses. Imputation of data for calculation of average (AUC) effects for FEV_1 will be described in the statistical analysis plan. No other imputation of missing data will be performed.

All available data from all patients who have received study treatment will be listed and summarised. Any unscheduled or unplanned readings will be presented within the patient listings, but only the scheduled readings will be used in any summaries. If a visit is rescheduled due to variability in FEV_1 or other reason, the rescheduled visit will be listed and summarised as the valid visit.

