6.4.6 Pharmacodynamic Analysis

6.4.6.1 Spirometry

For FEV_1 the average effect, (E_{av}), will be calculated as the Area Under the Curve (AUC) divided by the length of the time interval of interest. The AUC will be computed using the linear trapezoidal rule. Linear interpolation/extrapolation will be used to fill in a missing value (at most one missing value allowed) at end of the computational interval prior to calculation. In addition, the peak effect on FEV_1 will be computed as the maximum value (E_{max}) within 4 hours post-dosing. In analysis, E_{av} and E_{max} will be normalized using the baseline value.

Computed pharmacodynamic parameters for FEV_1 will be compared between placebo and the two doses of RPL554 using analysis of covariance (ANCOVA) models with fixed factors for treatment, period and patient, and using the baseline of the day as a covariate. FEV_1 will be analysed using multiplicative models, which means that data is logged prior to analysis and the result then transformed back to the linear scale giving treatment differences as ratios of geometric means. All three pairwise comparisons will be stated and expressed as the geometric mean ratio with 95% confidence interval and associated, 2-sided, p-value.

All spirometry data will be listed and summarized by treatment and assessment point as well as the change from baseline. Pharmacodynamic parameters will be

summarized by treatment. Graphics will include individual and mean FEV₁ and FVC curves over time (expressed as change from baseline on absolute scale) and scatter plots of computed pharmacodynamic parameters with the mean levels indicated.

Onset of effect will be defined as time to reach a 10% increase in FEV₁ counted from start/end of nebulization. Patients not reaching a response after 2 hours will be censored. Outcome will be illustrated using a Kaplan-Meier plot and, if appropriate, the median time to onset by (active) treatment group determined.

Duration of effect will be assessed by consecutively testing effect of active treatment versus placebo for increasing time points using similar models as the analysis of the pharmacodynamics parameters. If missing values exist, these will be filled in using linear interpolation/extrapolation prior to analysis.

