6.6 Statistical Issues

All hypothesis testing will be done using two-sided alternative hypotheses. P-values less than 5% will be considered statistically significant.

No adjustment for multiple testing will be done. A closed testing procedure will be applied: first the higher dose of RPL544 will be tested versus placebo and then, if statistically significant, the lower dose of RPL554 versus placebo. Finally the two doses of RPL554 will be compared.

Patients withdrawn after only one treatment period will not be included in the efficacy analyses. No imputation of missing data other than described under Section 6.4 will be performed.

Sensitivity analyses of pharmacodynamic data will be done to explore the impact of outliers or, for FEV₁ parameters, the use of rescue medication during the clinic visits.

All available data from all patients who have received study treatment will be listed and summarised. Any unscheduled or unplanned readings will be presented within the patient listings, but only the scheduled readings will be used in any summaries. If a visit is rescheduled due to variability in FEV₁ or other reason, the rescheduled visit will be listed and summarised as the valid visit.

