6.8 Changes in the Conduct of the Study or Planned Analyses

Clinical Study Protocol version 2.2 stated that the pharmacokinetic parameters should include AUC_{0-∞}, C_{max}, T_{max} and the terminal half-life, t_{1/2}. Due to the sampling scheme was considered insufficient to capture an appropriate t_{1/2} estimate, this parameter was omitted and AUC_{0-∞} was replaced with an AUC₀₋₂₄ (area under the scheduled sampling period).

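### The SAP fills missing FEV1 values in the duration tests without limit, although the protocol permits imputation only for AUC effects; a missing 24 h value would be projected 16 h along an undefined line.

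*SAP*

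**What the plan says.** SAP 6.4.6.1 assesses duration of effect by "consecutively testing effect of active treatment versus placebo for increasing time points", using models like those for the FEV1 parameters. It then adds: "If missing values exist, these will be filled in using linear interpolation/extrapolation prior to analysis". It gives no maximum number of filled values, no maximum distance, no anchor points and no scale (litres or log).

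The same section has a separate rule for the FEV1 AUC. That rule fills a value at the end of the computational interval and is capped: "at most one missing value allowed".

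Protocol 10.4.8 delegates one item to the SAP, which begins "Imputation of data for calculation of average (AUC) effects for" FEV1, and then closes the matter: "No other imputation of missing data will be performed".

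SAP 6.6 states: "No imputation of missing data other than described under Section 6.4 will be performed". This makes the duration rule visible but also endorses it. SAP 6.8, the section for changes to planned analyses, reports only the pharmacokinetic change ("Due to the sampling scheme was considered insufficient to capture an appropriate" half-life estimate). It does not mention imputation in the duration tests.

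**The concern.** Tests of FEV1 at single time points are not AUC effects, so the SAP rule falls outside what the protocol delegated, and the departure is not declared.

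The exposed time point is 24 h. It needs a return visit the next morning, nothing is measured between 8 and 24 h, and no later reading exists, so a missing value can only be extrapolated. A visit without it can still enter the analysis. Full analysis set membership (SAP 6.2) requires computable FEV1 parameters on at least two visits, and those parameters use data to 8 h at most. Table 14.2.2.4 (SAP 8.1) reports FEV1 by assessment point on that set.

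At stake is a 24 h comparison that depends on a programming choice the SAP does not make, and possibly a much noisier estimate whose reported standard error is too small.

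**Working it through.** The plan has no power, effect size or SD to reproduce; SAP 6.5 calls the sample size one of convenience.

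**Inputs from the documents.** Post-dose spirometry at 0.25, 0.5, 1, 2, 4, 6, 8 and 24 h (Protocol 7.2.1; SAP 4.4.1 adds 5 minutes). Ten completers. ANCOVA on log FEV1 with treatment, period, patient and baseline of the day. Two-sided 5%.

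**Assumptions.** Within-patient log SD 5%; equal correlation ρ between readings of one visit, varied from 0 to 0.9; line fitted on the log scale; 1.5 mg effect half the 6 mg effect; 4000 to 8000 simulated trials per scenario.

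**Step 1: the projected value.** The gap is 24 − 8 = 16 h. Through the last two readings, x24 = x8 + (x8 − x6)·16/2 = 9·x8 − 8·x6. Its SD relative to one reading is √(81 + 64 − 144ρ) = √(145 − 144ρ). The least-squares line through the seven readings from 0.25 to 8 h has 24 h weights −0.968, −0.871, −0.676, −0.288, 0.490, 1.268 and 2.045.

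| ρ | 6–8 h line | all-readings line |
|---|---|---|
| 0 | 12.0 | 2.9 |
| 0.5 | 8.5 | 2.2 |
| 0.7 | 6.6 | 1.8 |
| 0.9 | 3.9 | 1.3 |

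Interior interpolation does not add noise. At ρ = 0 the multiplier is 0.71 for 6 h from 4 and 8 h, and 0.90 for 8 h from 6 and 24 h.

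**Step 2: the choice of line can change the sign.** Take an effect of 8% up to 6 h, 6% at 8 h and none at 24 h. The 6–8 h line gives 9·ln 1.06 − 8·ln 1.08 = −0.0913, a ratio of 0.913 (−8.7%). The all-readings line gives 2.045·ln 1.06 − 1.045·ln 1.08 = +0.0387, a ratio of 1.039 (+3.9%). The truth is 0. On a mean of 10 these are about −0.9% and +0.4%.

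**Step 3: power at 24 h.** One 6 mg value missing, constant 6% effect:

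| ρ | complete | observed only | filled, 6–8 h line |
|---|---|---|---|
| 0 | 63% | 59% | 34% |
| 0.5 | 75% | 71% | 47% |
| 0.7 | 90% | 87% | 58% |

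With the all-readings line (separate runs), observed versus filled is 60% vs 57%, 72% vs 70% and 87% vs 86%.

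**Step 4: precision.** With the 6–8 h line and one value filled, the SD of the 6 mg versus placebo estimate is 2.1 to 2.7 times that on observed values at ρ from 0 to 0.7. The model SE is too small: true SD 6.6% vs SE 5.6%, 4.9% vs 4.1% and 3.8% vs 3.3% at ρ = 0, 0.5 and 0.7.

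**Step 5: bias (6–8 h line).** For the waning curve of step 2 with one 6 mg value missing, the bias is −0.9%. If FEV1 drifts +4%, +2% and 0% at 6, 8 and 24 h in all arms and one placebo value is missing, the filled value is off by 9·ln 1.02 − 8·ln 1.04 = −0.136. On a mean of 10 this favours 6 mg by about 1.4% (simulated 1.3% to 1.4%). So the bias can go either way.

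**Step 6: type I error (6–8 h line, ρ from 0 to 0.9).** One missing value 3.5% to 5.1%; two 5.2% to 5.8%; three on one arm 7.1% to 8.1%; observed values 4.4% to 5.6%. The rise with three depends on which patients have the gaps. With one fixed set of three patients at ρ = 0.5 it was not seen (4.9%).

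**Step 7: scale.** On the litre scale the 6–8 h line gives a non-positive value, which cannot be logged, when ln(x6/x8) ≥ ln(9/8). With no effect this has probability 4.8%, 0.9% and 0.1% at ρ = 0, 0.5 and 0.7, so it is mainly a problem when errors are close to independent.

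**The case against.** The strongest reply concerns reach.

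- **A constant 6% effect to 24 h is optimistic.** Protocol 1.1 gives a half-life of 8 to 13 hours and describes the formulation as suited to twice daily dosing. If the effect has gone by 24 h, the bias for a missing 6 mg value is −0.9%, against a claim of duration, and with one gap the type I error is not inflated. This stands. The power figures show the cost if an effect persists, and the loss of precision remains either way.
- **24 h may not be tested.** The SAP names no last time point. If testing stops at the first non-significant point, which it does not say, 24 h is reached only after every earlier success. This stands as a limit on scope. Table 14.2.2.4 nevertheless plans the analysis by assessment point.
- **Gaps should be few.** Ten patients must complete to 24 h and non-completers are replaced (SAP 3.3), and no missing-data rate is given. Three gaps on one arm is a stress case. Replacement adds a patient, however; it does not remove the replaced one from the full analysis set.
- **The main harm depends on the line.** With all readings and one gap the power loss is 1 to 3 points. True, but the SAP does not say which line applies.
- **Safeguards exist.** Data can be excluded before lock (SAP 6.2), deviations are reported (Protocol 10.1), and SAP 6.6 promises: "Sensitivity analyses of pharmacodynamic data will be done to explore the impact of outliers". These can reduce the problem or expose it, but they leave the rule in place.
- **Protocol version.** The SAP cites version 4.0, and the version of the protocol text reviewed cannot be confirmed. Nothing indicates that 10.4.8 changed.
- **A narrower fix would do.** Interior interpolation is harmless for noise and could be kept if capped and declared. That is a fair alternative, but it would still contradict Protocol 10.4.8 unless declared as a change.

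**Conclusion.** The concern holds. The contradiction between SAP 6.4.6.1 and Protocol 10.4.8 is textual and needs no assumption, and neither does the absence of a cap, a distance limit or a defined line.

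The size of the effect does rest on assumptions: 10 patients, 5% log SD, a log-scale line and equal within-visit correlation. Under the 6–8 h reading, one filled 24 h value on 6 mg more than doubles the SD of the estimate at correlations up to 0.7. It also costs about 24 to 29 percentage points of power relative to observed values (59 − 34 = 25, 71 − 47 = 24, 87 − 58 = 29). Under the all-readings line, one gap costs little. Type I error is not a concern with one gap and rises only modestly in the three-gap stress case.

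This affects one late time point of a secondary endpoint and does not touch the primary pharmacokinetic analysis. It should be corrected, but it does not threaten the trial's main conclusion.

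**What to change.** In SAP 6.4.6.1, delete the fill-in sentence for the duration analysis and write instead: *Each time point is analysed on observed values; missing values are not filled in.* Keep the planned ANCOVA with treatment, period, patient and baseline of the day. Leave the capped end-of-interval rule for the AUC unchanged, because Protocol 10.4.8 delegates that rule to the SAP.

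The cost is one sentence. A visit with a missing reading drops out of that one time point only. With one 6 mg value missing, power for a 6% effect is 59% instead of 63% with complete data at correlation 0, 71% instead of 75% at 0.5, and 87% instead of 90% at 0.7. Harmless interior interpolation is given up too, solely to agree with the protocol.

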6.4.6.2 Sputum inflammatory mediators, rheology and exhaled breath pH

Il-8, TNF- α , MPO, exhaled breath pH and sputum viscoelasticity (log G) collected 6 and 24 h after dose administration will be compared between treatments using similar ANCOVA models as for the FEV₁ parameters. Multiplicative models will be used for the sputum inflammatory mediators, additive (linear) models for exhaled breath pH and sputum viscoelasticity (log G) that already are expressed on log scales.

All data will be listed and summarized by treatment and assessment point as well as the change from baseline. Graphics will include individual and mean value curves over time for each variable.

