6.2.3 Post-Dose Assessments

- 12-lead ECGs at 1, 2, 4 and 8 hours
- Vital signs at 30 minutes and 1, 2, 4, 6 and 8 hours
- Blood samples for pharmacokinetics at 15, 30 minutes and 1, 2, 4, 6, 8 and 24 hours
- Spirometry at 15 and 30 minutes and 1, 2, 4, 6, 8 and 24 hours
- Questioning for adverse events
- Exhaled breath pH at 8 and 24 hours (UK centre only)
- Sputum obtained for rheology and inflammatory mediator measurement at 8 and 24 hours

Patients completing the visit will be instructed to return in 3 to 14 days for Visit 3.

6.3 Visit 3 to 4

Patients must withhold short and long acting bronchodilators prior each visit as defined in Section 5.9.1. Patients should fast from 2 hours pre-dose until 2 hours post-dose (except for water) and other restrictions defined in Section 5.4.2 should be adhered to. The following assessments will be performed:

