6.3.3 Post-Dose Assessments

- 12-lead ECGs at 1, 2, 4 and 8 hours
- Vital signs at 30 minutes and 1, 2, 4, 6 and 8 hours
- Blood samples for pharmacokinetics at 15, 30 minutes and 1, 2, 4, 6, 8, 12 and 24 hours
- Spirometry at 15 and 30 minutes and 1, 2, 4, 6, 8 and 24 hours
- Questioning for adverse events
- Exhaled breath pH at 8 and 24 hours (UK centre only)
- Sputum obtained for rheology and inflammatory mediator measurement at 8 and 24 hours

Patients completing Visit 3 will be instructed to return in 3 to 14 days for Visit 4. Patients completing Visit 4 will be instructed to return in 3 to 10 days for Visit 5.

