7.2.2 Sputum Measurements

Sputum samples will be taken pre-dose and at 8 and 24 hours post-dose at Visit 2 to Visit 4 by spontaneous expectoration over no more than 5 minutes and transported on ice for rapid processing (collection to storage within 30 minutes). Whole sputum will be immediately frozen at -20°C and then transferred to -80°C for storage prior to analysis (Horsley et al, 2014).

Rheological analysis will be performed before and after incubation at 37°C for 60 minutes (Horsley et al, 2014). Inflammatory mediators (IL-8, TNF- α and MPO) will be measured according to the published methodology (Downey et al, 2007).

Results will be provided to the Investigator for entry into the CRF.

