3 OVERALL STUDY DESIGN

3.1 Overview of Study Design

This is a Phase IIa, randomised, double blind, placebo controlled, complete block three way crossover study to investigate the pharmacokinetics of nebulised RPL554 (1.5 mg and 6 mg) in adult patients with CF. It is planned to enrol sufficient patients to assure that 10 patients complete all three treatment periods at one centre in the UK. The study comprises five visits: screening (Visit 1), three treatment visits (Visit 2 to Visit 4) and an end of study visit (Visit 5). Patients will be screened for eligibility (Visit 1), including a reversibility test with salbutamol, between 3 and 14 days prior to the first dose of study treatment.

Eligible patients will then attend for three separate 1 day treatment visits (Visits 2 to Visit 4) each separated by a at least a 3-day washout period. Patients will be randomised pre-dose at Visit 2. Patients will receive a single nebulised dose of 1.5 mg RPL554 or 6 mg RPL554 or placebo at each visit. The pre-dose FEV₁ at Visit 3 and Visit 4 must be within $\pm 20\%$ of the pre-dose FEV₁ at Visit 2 in order to ensure consistent baseline FEV₁ for each study treatment. At each visit, patients will be resident at the study centre from the morning until at least 8 hours after dosing.

Patients will be discharged after 8 hours, but return the following morning for final assessments 24 hours after dosing.

The following will be performed at each treatment visit:

- Measurements of lung function (FEV₁ and forced vital capacity [FVC]) pre-dose and up to 24 hours post-dose
- Blood sampling pre-dose and up to 24 hours post-dose for pharmacokinetic analysis
- Sputum sampling pre-dose and at 8 and 24 hours post-dose for rheology and measurement of inflammatory mediators (interleukin 8 [IL-8], tumour necrosis factor alpha [TNF- α], myeloperoxidase [MPO])
- Exhaled breath pH measurement pre-dose and at 8 and 24 hours post-dose
- Urine pregnancy test pre-dose (female patients only)
- Vital signs and 12-lead electrocardiogram (ECG)s pre-dose and up to 8 hours post-dose

An end of study visit (Visit 5) will be performed 3 to 10 days after the last dose of study treatment. Adverse events will be recorded throughout the study and laboratory safety tests, a physical examination and urine pregnancy tests (female patients only) will be performed at screening (Visit 1) and at the end of study visit (Visit 5).

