4.4.2 Sputum Inflammatory Mediators

Sputum samples will be taken pre-dose and at 8 and 24 hours post-dose at Visit 2 to Visit 4 by spontaneous expectoration over no more than 5 minutes and transported on ice for rapid processing (collection to storage within 30 minutes). Whole sputum will be immediately frozen at -20°C and then transferred to -80°C for storage prior to analysis (Horsley et al, 2014).

Rheological analysis will be performed before and after incubation at 37°C for 60 minutes (Horsley et al, 2014). Inflammatory mediators (IL-8, TNF- α and MPO) will be measured according to the published methodology (Downey et al, 2007).

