4.4.3 Exhaled Breath pH

Exhaled breath pH will be measured pre-dose and at 8 and 24 hours post dose at Visit 2 to Visit 4. Exhaled breath pH measurement will be performed in accordance with the method described by MacNee et al, 2011. In brief, exhaled breath condensate (EBC) samples will be collected during tidal breathing for 10 minutes, without nose clips, using the RTube™ (Respiratory Research Inc., Charlottesville, Virginia). A 200 μ L aliquot of EBC will be used for the pH assay. Measurement of pH will be performed after deaeration by bubbling argon through the sample at 2 L/min while monitoring pH until the reading stabilised, usually after 8 minutes of deaeration with argon.

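### SAP 6.4.6.2 compares sputum markers and breath pH at 6 and 24 h, but they are sampled only pre-dose and at 8 and 24 h

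*SAP*

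**What the plan says.** The analysis rule is in SAP 6.4.6.2. Five variables (IL-8, TNF-α, MPO, exhaled breath pH and sputum viscoelasticity as log G) "collected 6 and 24 h after dose administration will be compared between treatments using similar ANCOVA models", on a multiplicative scale for the three mediators and an additive scale for the other two.

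The sampling times are stated elsewhere in the same SAP:

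- Section 3.1: "Sputum sampling pre-dose and at 8 and 24 hours post-dose for rheology and measurement of inflammatory mediators". The same list gives 8 and 24 h for breath pH.
- Section 4.4.2: "Sputum samples will be taken pre-dose and at 8 and 24 hours post-dose at Visit 2 to Visit 4".
- Section 4.4.3: "Exhaled breath pH will be measured pre-dose and at 8 and 24 hours post dose".

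The protocol agrees with these sampling sections. Section 7.2.2 reads "Sputum samples will be taken pre-dose and at 8 and 24 hours post-dose at Visit 2 to Visit 4 by spontaneous expectoration", and Section 7.2.3 gives the same times for breath pH. The Visit 2 list in Section 6.2.3 has "Sputum obtained for rheology and inflammatory mediator measurement at 8 and 24 hours", and the Visit 3 to 4 list in Section 6.3.3 has "Exhaled breath pH at 8 and 24 hours (UK centre only)". The synopsis and Section 3.1 say the same.

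**The concern.** The sentence that defines the treatment comparison names a time at which nothing is collected, and leaves out a time at which samples are collected. Within the SAP, this ANCOVA is the only treatment comparison serving the exploratory anti-inflammatory objective. An analyst who follows the text can test only 24 h. An analyst who tests 8 h instead departs from the written plan, and Protocol 10.1 requires any such departure to be reported and justified in the study report.

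The slip could also pass unnoticed into table shells or programs, because 6 h is a genuine time point in this study for spirometry, pharmacokinetic blood samples and vital signs. If the discrepancy is found only after unblinding, a reader could ask whether the 8 h comparison was chosen with the results in view. SAP 6.6 makes no adjustment for multiple testing, which gives that question more weight.

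**Working it through.** The plan gives no figure to reproduce here, since the sample size is one of convenience. The check sets the analysis times against the sampling times and then counts.

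**Times side by side**

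| Source | Sputum, post-dose | Breath pH, post-dose |
|---|---|---|
| SAP 6.4.6.2 (analysis) | 6, 24 h | 6, 24 h |
| SAP 3.1 | 8, 24 h | 8, 24 h |
| SAP 4.4.2 and 4.4.3 | 8, 24 h | 8, 24 h |
| Protocol synopsis and 3.1 | 8, 24 h | 8, 24 h |
| Protocol 6.2.3 and 6.3.3 | 8, 24 h | 8, 24 h |
| Protocol 7.2.2 and 7.2.3 | 8, 24 h | 8, 24 h |

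The column positions of Protocol Table 2 are not readable in the text I worked from, so I place no weight on that table. The visit-by-visit lists are clear without it.

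**Overlap.** Analysed {6, 24} against sampled {8, 24} leaves only {24}. The 6 h analysis has no scheduled sample, and the 8 h sample has no specified analysis.

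**Count**

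- Variables named in SAP 6.4.6.2: 5. Analyses: 5 × 2 times = 10. Without scheduled data: 5 × 1 = 5, and 5/10 = 50%.
- SAP 4.4.2 adds a complication for log G: "Rheological analysis will be performed before and after incubation at" 37°C. Section 6.4.6.2 does not say which value is used. If both are analysed: 6 × 2 = 12, of which 6 have no scheduled data, and 6/12 = 50%.
- The same number of possible 8 h analyses, 5 or 6, is left unspecified.

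**Does anything else in the plan supply the missing piece?**

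- SAP 6.8, which records changes to planned analyses, covers only the pharmacokinetic parameters. A move to 6 h is not declared there.
- SAP 6.6 keeps unscheduled readings out of the summaries and allows no imputation beyond that described in Section 6.4. The interpolation rules in Section 6.4 are in the spirometry subsection (6.4.6.1), so a 6 h biomarker value cannot be derived under the plan.
- The planned statistical tables 14.2.3.2 and 14.2.3.3 in SAP 8.1 name no time point.
- SAP 6.4.6.2 and the graph list in 8.2 bring the 8 h data into listings, summaries and plots, but not into a test.
- The protocol synopsis assigns biomarkers and breath pH to a t test without naming a time point or contrast, so it does not settle the matter.

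**After correction.** With 8 in place of 6, all 10 of 10 analyses have a scheduled post-dose value and a same-day pre-dose baseline for the covariate.

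**The case against.** The strongest reply is that this is a one-character slip with one obvious correction. The only post-dose sample other than 24 h is at 8 h. The model, scale and analysis set are already specified, and the planned statistical tables carry no time restriction. On that reading no sample and no analysis is lost, and 5 of 10 merely restates one of two time points. The stakes are also low: the mediators and rheology are exploratory, breath pH is in no endpoint list, no decision rule depends on these tests, and the 24 h comparisons and all descriptive output stand.

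Most of this is right, and it limits the importance of the point. It does not remove it. The sentence in 6.4.6.2 is the pre-specification itself, and no other part of the SAP names 8 h for a treatment comparison. Tables without a time label are compatible with 8 h but do not commit to it.

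Two further replies carry less weight. First, the supplied protocol may not be version 4.0, on which the SAP says it is based: the SAP describes one UK centre, the protocol two centres. That weakens the protocol comparison but not the conflict inside the SAP. Second, the digit could have been misread when the file was converted to text. The sentence otherwise reads cleanly and nothing shows a misreading; a look at the SAP itself settles it.

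**Conclusion.** The point holds. SAP 6.4.6.2 specifies comparisons at a time when these variables are not sampled, and specifies none at 8 h, when they are. Taken literally, half of the specified variable-by-time analyses (5 of 10, or 6 of 12 if log G is analysed before and after incubation) have no scheduled data. The share is half on either count.

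The conclusion rests on the SAP's own text and does not depend on the protocol version. That 8 h was intended is an inference, though a strong one. The effect is confined to the exploratory sputum mediators and rheology and to breath pH. The primary pharmacokinetic analysis and the FEV₁ analyses are untouched. It should be corrected because the error is in the operative analysis rule and the correction costs almost nothing.

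**What to change.** Before unblinding, change 6 to 8 in SAP 6.4.6.2 so that the comparison is made at 8 and 24 h. This is one number in the SAP, with no new data or procedures. While the sentence is open, it could also say whether log G is the value before incubation, after it, or both.

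A separate, minor consistency check: SAP 4.4.1 lists a 5-minute post-dose spirometry that Protocol 6.2.3, 6.3.3 and 7.2.1 do not schedule. This may be a difference between protocol versions, and no effect on the FEV₁ results is claimed. The list should be reconciled with the protocol version in force, which means comparing one time-point list with another.
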